3.6 Randomization Method

Women will be randomized to either an inpatient or outpatient cervical ripening procedure using a computer generated randomization scheme through REDCap.

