5.1 Data Relevant to the Primary Outcome

5.1.1 Sample Size and Power

- 1. 200 women randomized to two groups for comparison will be enrolled in the study to participate in the research group (receiving Cervidil insert). Data will be collected on the comparison group (all patients admitted cervical ripening and induction of labor) during the same time period.
- 2. With 200 patients in each group a standard two sample t test has 95% power to detect a difference of 0.36 times the standard deviation and 80% power to detect differences of 0.28 times the standard deviation. For example, if the mean time from admitting to delivery is 10 hours with a standard deviation of 2 hours (meaning that most (95%) times are in the range from 6 to 14 hours) then with this sample size we would have 95% power to detect a reduction of 43.2 minutes in the treatment group and a 80% power to detect a difference of 33.6 minutes. These numbers will differ if the true standard deviation is different from 2 hours.

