5.3 Analysis Plan

Primary analysis will be done using 2 sample t-tests on the numeric outcomes with the possibility of using the log of the outcome when the outcome is skewed (as is common for waiting times and cost variables). If the data is not sufficiently normal after logging, then a 2 sample permutation test on the means will be used instead. For categorical outcomes (e.g. delivery type) a chi-squared test will be used to compare the proportion in each category between the treatment and control groups. All tests will be performed at a 5% significance level. The p-values will be reported both unadjusted for multiple outcomes and also adjusted using the False Discovery Rate method. Conclusions will be made using the unadjusted values since each outcome is of interest by itself and they are predetermined.

Additional exploratory data analysis will be done using linear model including regression and logistic regression to adjust for other variables of interest. Any interesting results will be reported as exploratory with need for confirmation since the potential results are not on a predetermined list.

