6.3 Performance Monitoring

The following data elements will be collected.

- Participant ID
- Age
- EDC
- Method of Dating
- G/TPAL
- Date/Time
 - Hospital evaluation
 - Bishop score prior to placement of cervidil insert
 - Bishop score on admission upon removal of Cervidil insert
 - Time of insertion
 - Time Home
 - Time of readmit
 - Reason for readmit (see above reasons to return to L&D)
 - Time of removal of Cervidil insert
 - Time Pitocin started
 - Epidural- if placed and if so when
 - Delivery time
 - Method of delivery
 - Spontaneous vaginal
 - Operative vaginal
 - C-Section
 - Indication if other than spontaneous vaginal delivery
- Apgar, weight, cord pH if done

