7.1.1 Participating Clinical Centers

Dixie Regional Medical Center, labor and delivery unit, and Utah Valley Hospital, labor and delivery unit will conduct this study.

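### The primary t-test in section 5.3 is valid but gives up precision, because adjustment for baseline variables the trial records or knows is left exploratory

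*Combined protocol and SAP*

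**What the plan says.** Section 5.3 sets the confirmatory test: "Primary analysis will be done using 2 sample t-tests on the numeric outcomes". Skewed outcomes may be logged, and a permutation test on the means is the fallback if logging is not enough. Covariates appear only afterwards: "Additional exploratory data analysis will be done using linear model including regression and logistic regression to adjust for other variables of interest". The variables are not named, and the weight of such results is limited in advance: "Any interesting results will be reported as exploratory with need for confirmation since the potential results are not on a predetermined list".

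Section 6.3 lists the obstetric history code that gives parity (G/TPAL) and "Bishop score prior to placement of cervidil insert". Site is not on that list, but section 7.1.1 names two hospitals: "Dixie Regional Medical Center, labor and delivery unit, and Utah Valley Hospital, labor and delivery unit will conduct this study". Section 3.6 describes allocation only as "using a computer generated randomization scheme through REDCap", with no mention of stratification. Section 2.1 treats an unfavorable cervix as raising the risk of cesarean and of labor beyond 24 hours, without giving a correlation or a variance share.

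**The concern.** An unadjusted comparison leaves in the error term whatever part of the outcome variance is predictable from parity, cervical status and hospital. If those variables predict time to complete dilation or cost, the confidence interval is wider than it needs to be and power is lower.

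The plan cannot recover this later. Under section 5.3 an adjusted result is exploratory and awaits confirmation, so it cannot support the primary conclusion even if the arms happen to differ on parity or cervix. With no stratification described, nothing else in the plan limits such chance differences. The variables are cheap to use, and at 100 women per arm precision is not plentiful.

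**Working it through.** **Inputs.** Test level: "All tests will be performed at a 5% significance level" (section 5.3). Test: "a standard two sample t test" (section 5.1.1). Sidedness is not stated; two-sided is assumed. Effects: 0.36 SD paired with 95% power and 0.28 SD with 80% (section 5.1.1). Example SD: 2 hours, or 120 minutes (section 5.1.1). Sample size: 200 per group in section 5.1.1, 100 per arm in section 2.2. R², the share of within-arm outcome variance explained by the covariates, is not in the documents; it is assumed, over 0.05 to 0.30.

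**Step 1: reproduce the plan's figures.** With n per group and δ in SD units, power ≈ Φ(δ/√(2/n) − 1.960).
- n = 200, δ = 0.36: 0.36/0.100 = 3.60; Φ(1.64) = 95.0%.
- n = 200, δ = 0.28: 0.28/0.100 = 2.80; Φ(0.84) = 80.0%.
- 0.36 × 120 = 43.2 minutes and 0.28 × 120 = 33.6 minutes.

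All agree with section 5.1.1. One-sided testing would give 97.5% and 87.6%, so two-sided is the reading that fits.

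**Step 2: the same test at the randomized size.** For n = 100, √(2/100) = 0.1414.
- δ = 0.36: 0.36/0.1414 = 2.546; power 72.1%.
- δ = 0.28: 0.28/0.1414 = 1.980; power 50.8%.
- Detectable with 80% power: (1.960 + 0.842) × 0.1414 = 0.396 SD, or 47.5 minutes at the example SD.

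**Step 3: add baseline covariates.** A linear model with prognostic covariates reduces the residual SD by the factor √(1 − R²), so power ≈ Φ(δ/√(2(1 − R²)/n) − 1.960), and the effective sample size is multiplied by 1/(1 − R²). Example, R² = 0.20, δ = 0.36: 0.1414 × 0.894 = 0.1265; 0.36/0.1265 = 2.846; power 81.2%.

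| Assumed R² | Effective n | Power at 0.36 SD | Power at 0.28 SD | Detectable at 80% power |
|---|---|---|---|---|
| 0 | ×1.00 | 72.1% | 50.8% | 0.396 SD (47.5 min) |
| 0.05 | ×1.05 | 74.3% | 52.8% | 0.386 SD (46.3 min) |
| 0.10 | ×1.11 | 76.5% | 55.1% | 0.376 SD (45.1 min) |
| 0.20 | ×1.25 | 81.2% | 60.0% | 0.354 SD (42.5 min) |
| 0.30 | ×1.43 | 86.1% | 65.8% | 0.331 SD (39.8 min) |

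These use the normal approximation. The noncentral t gives values at most about half a point lower: 71.7%, 73.9%, 76.1%, 80.8% and 85.7% at 0.36 SD, and 50.4% at 0.28 SD without adjustment.

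**Step 4: can adjustment make up for 100 rather than 200 per arm?** That needs 100/(1 − R²) = 200, so R² = 0.50, above the range considered.

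**Step 5: is the Bishop score available in both arms?** Section 6.3 lists it before placement for everyone. Section 4.2.1 step 3 has it documented at the outpatient examination. Section 4.2.2 step 4 calls for the inpatient examination but does not mention documenting the score there; the inpatient steps mention it only with removal (step 7). Section 4.2 also places randomization normally at scheduling, so the score is usually taken after allocation, and no blinding is described.

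**The case against.** The strongest reply is that nothing here is an error. Under randomization the unadjusted t-test is valid, and its type I error rate already allows for chance imbalance. Section 5.3 is also coherent in treating predetermined tests as confirmatory and unnamed models as exploratory. This stands. A reader might infer that the primary test is biased, or that an imbalance in parity would invalidate it; the documents do not support that.

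Second, the gain rests on an assumed R². Only cervical status has prognostic support in the text, and only qualitatively; for parity and site it is a reviewer's expectation. All participants are planning ripening with a cervix under 3 cm at placement, which may narrow the Bishop range and lower R². At R² of 0.05 the gain is about two points. This stands too, and is why the table starts there.

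Third, 0.36 SD flatters the case. The plan pairs that difference with 95% power; its 80% benchmark is 0.28 SD, where adjustment reaches only 60% to 66% at R² of 0.20 to 0.30. A reader might infer that adjustment restores the planned power. It does not.

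Fourth, power may not be the constraint for the time outcome. Inpatients receive admission status before placement and outpatients on return for induction (sections 4.2.1 and 4.2.2), so much of the ripening period falls inside only one arm's interval. At the example SD, a 2-hour difference is 1 SD, for which the unadjusted test has over 99.9% power. This limits what adjustment adds for time if the difference is that large. It does not settle the matter for cost, the other primary outcome in section 4.4.1.

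Finally, it is tempting to call this a change of wording with every covariate in hand. Step 5 shows that it is not quite that.

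**Conclusion.** The point holds as avoidable inefficiency in the choice of primary analysis. Section 5.3 gives up precision by leaving exploratory the baseline variables that the trial lists or knows. At 100 per arm the gain runs from about 2 percentage points of power (R² 0.05) to about 14 at 0.36 SD or 15 at 0.28 SD (R² 0.30). In sample-size terms that is about 5% to 43% more women. These figures assume a two-sided 5% test, 100 analyzed per arm and an R² that the documents do not supply, so the direction is firmer than the size. The mismatch between sections 5.1.1 and 2.2 is a separate and larger problem, and remains open whether or not this change is made.

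**What to change.** In section 5.3, prespecify the primary analysis of each numeric outcome as a linear model with arm, parity (nulliparous or parous), site and pre-placement Bishop score. Fit it on whichever scale the section's existing rule selects, raw or log. Where that rule would fall to a permutation test, use a permutation test of the arm effect from the same model. Report the unadjusted t-test as supportive. Make the change before any outcome comparison by arm is seen, bearing in mind the six-monthly interim analyses in section 5.4.

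Align the inpatient steps in section 4.2.2 with sections 4.2.1 and 6.3, so that the Bishop score is documented before placement in both arms. State in advance how a missing score is handled. Because the score is usually recorded after open allocation, also report the model with parity and site only as a sensitivity analysis. Add site to the data elements in section 6.3.

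The cost is an amendment to the analysis text, one documentation instruction in the inpatient procedure and one extra data field. No added recruitment is needed. Stratifying the allocation would be a separate change to the randomization set-up, and this fix does not depend on it. Sections 5.1.1 and 2.2 must still be reconciled on the sample size.

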5.4 Interim Analysis

Each adverse outcome will be reviewed within 24 hours of report by the PI. In the event that the PI is unavailable, the adverse outcome may be reviewed by any of the other physician investigators.

Interim analysis will be done every 6 months until completion of the study. The study investigators may perform an interim analysis at any time if they suspect a higher adverse outcome than anticipated.

6 – DATA COLLECTION

6.1 Data Collection Forms

The data collection forms will include a 24 item study specific survey consisting of questions from the previously validated DoD/VA pain Supplemental Questions scale, study specific questions, and a 32 item survey to be completed by all patients seen at Intermountain.

- DoD/VA Pain Supplemental Questions (Cleeland & Ryan, 1994)
- HCAHPS (HCAHPS Fact Sheet. June, 2015, http://www.hcahpsonline.org/Facts.aspx)

6.2 Web Data Entry System

This study will utilize the REDCap data management system. This system will reside behind Intermountain Healthcare firewalls and is CFR Part 11 compliant.

6.3 Performance Monitoring

The following data elements will be collected.

- Participant ID
- Age
- EDC
- Method of Dating
- G/TPAL
- Date/Time
 - Hospital evaluation
 - Bishop score prior to placement of cervidil insert
 - Bishop score on admission upon removal of Cervidil insert
 - Time of insertion
 - Time Home
 - Time of readmit
 - Reason for readmit (see above reasons to return to L&D)
 - Time of removal of Cervidil insert
 - Time Pitocin started
 - Epidural- if placed and if so when
 - Delivery time
 - Method of delivery
 - Spontaneous vaginal
 - Operative vaginal
 - C-Section
 - Indication if other than spontaneous vaginal delivery
- Apgar, weight, cord pH if done

6.4 Confidentiality and Data Protection

Confidentiality

Information is kept with study identification numbers to protect the identity of participants. Electronic data are protected on encrypted drives and databases (REDCap) that are only accessible to authorized research staff.

Paper documents are locked in research offices, accessible only to the study team.

Data Protection

REDCap and Intermountain servers are maintained by the Intermountain IS team. These are regularly backed up to ensure data integrity.

7 – STUDY ADMINISTRATION

7.1 Organization and Funding

Intermountain Healthcare. See attached budget requested from Ferring Pharmaceuticals.

7.1.1 Participating Clinical Centers

Dixie Regional Medical Center, labor and delivery unit, and Utah Valley Hospital, labor and delivery unit will conduct this study.

7.1.2 Funding

Funding will be provided by Ferring Pharmaceuticals

7.2 Data Safety Monitoring Committee

The Data Safety Monitoring Committee (DSMC) will be compromised of at least 3 members who are not affiliated with the trial to monitor the maternal and fetal outcomes in the study. The DSMC will evaluate study data from the first five participants, including any reported adverse events. Thereafter, they will meet on a quarterly basis throughout the remainder of the study enrollment period of the study.

7.2.1 Stopping Rules/Discontinuation Criteria

As per interim analysis above (5.4). The study can be discontinued at any time by the investigators or the DSMC if any of outcomes are less than anticipated and there is documented or a concern for patient harm.

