4.4.2 Maternal Secondary Outcomes

- Patient satisfaction as measured by patient satisfaction/pain/anxiety surveys.
- Vaginal delivery rate
- Operative Vaginal delivery rate.
- Cesarean delivery rate.
- Start of oxytocin until delivery
- Time of delivery until discharge
- Time of admission until discharge

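### The only study-level stopping criterion (7.2.1) joins outcomes falling below expectation to harm with an "and" that leaves harm alone outside it, and for adverse outcomes its direction does not match 5.4

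*Combined protocol and SAP*

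**What the plan says.** Section 7.2.1 first refers back to the interim analysis in 5.4. It then gives both bodies the same power: "The study can be discontinued at any time by the investigators or the DSMC". The condition attached to that power reads as follows: "if any of outcomes are less than anticipated and there is documented or a concern for patient harm".

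Section 5.4 provides for three things. The principal investigator, or another physician investigator in their absence, reviews each adverse outcome within 24 hours of report. There are regular looks: "Interim analysis will be done every 6 months until completion of the study". There are also optional extra looks: "The study investigators may perform an interim analysis at any time if they suspect a higher adverse outcome than anticipated".

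Section 7.2 sets up a committee of at least three members outside the trial, "to monitor the maternal and fetal outcomes in the study". It reviews data from the first five participants, including reported adverse events, and then meets quarterly. Section 7.2 gives it no decision criterion of its own.

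The outcomes are listed in 4.4, and the product risks (hyperstimulation with or without fetal distress, and fetal distress alone) in 2.4.1.

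**The concern.** A stopping criterion should say which finding is worrying and in which direction. This one looks wrong in two ways. It uses a single direction, *less*, for all outcomes, although for most safety outcomes more is worse. It also makes harm one half of a joint condition, when harm is what the committee exists to detect.

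The setting makes this more than a matter of style. Section 3.7.1 says that outpatient use is not an indication on the package insert and that an IND will be obtained. Under 4.2.1, outpatient participants go home with the insert in place. Section 2.2 says that the study is not powered for fetal or newborn mortality, so a serious event may well appear as a single case and not as a shift in an outcome. A committee facing such a case should not have to guess whether the written criterion covers it.

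**Working it through.** No arithmetic applies: neither 7.2.1 nor 5.4 gives a rate, threshold, boundary or significance level. The check compares wording and logic.

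**Step 1. The logic of 7.2.1.** Let A be that at least one outcome is less than anticipated, and B that harm is documented or is a concern. The criterion is A and B.

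| A | B | Criterion met? |
|---|---|---|
| no | no | no |
| yes | no | no |
| no | yes | **no** |
| yes | yes | yes |

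The third row is the gap: harm is present, no outcome is below expectation, and the criterion is not met.

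**Step 2. The direction of A.** Reading *less* literally:

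| Outcome or risk | Section | A lower value is |
|---|---|---|
| Hyperstimulation, fetal distress | 2.4.1 | favourable |
| "Cesarean delivery rate" | 4.4.2 | favourable |
| NICU admission and length of stay | 4.4.3 | favourable |
| Vaginal delivery rate | 4.4.2 | unfavourable |
| Patient satisfaction | 4.4.2 | unfavourable |
| 5-minute Apgar score | 4.4.3 | unfavourable |

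The wording therefore points the wrong way for the first three rows and the right way for the last three.

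**Step 3. Comparison with 5.4.** The trigger there is "if they suspect a higher adverse outcome than anticipated". For adverse outcomes this is the opposite direction to 7.2.1. The two triggers lead to different actions, however: 5.4 allows an unscheduled analysis, and 7.2.1 allows a stop.

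**Step 4. Does 5.4 fill the gap?** It sets a review time, a schedule and an option for extra looks. It does not say what finding would lead to stopping, so the cross-reference adds no criterion.

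**Step 5. Can A be evaluated?** Both sections refer to what is anticipated. Neither states an anticipated level for any adverse outcome, and no such rate appears elsewhere in the plan. The benchmark for A is therefore undefined.

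**The case against.** The strongest defence is that this is loose drafting which no sensible committee would misapply. *Less than anticipated* can be read as *worse than expected*, and the harm clause beside it supports that sense. The text speaks of outcomes in general, not of adverse outcomes. Other safeguards exist: physician review of each adverse outcome within 24 hours, reporting of serious adverse events to the FDA and the manufacturer within 24 hours (4.3), and quarterly DSMC meetings.

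Much of this stands, and it rules out several stronger readings that a reader might infer:

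- *That the rule blocks a stop for harm.* It does not. The verb is *can be*, and nothing says *only if*.
- *That no excess of harm could satisfy the rule.* This is too strong. One outcome is enough for the first limb, so fetal harm with lower Apgar scores would meet both limbs. So would excess cesarean delivery with a concern for harm, because the vaginal delivery rate falls.
- *That it allows a stop merely because results are better than planned.* It does not, because the second limb still requires harm or a concern for it.
- *That 7.2.1 flatly contradicts 5.4.* The two sections govern different actions and both can be followed. The fault is an inconsistency of direction between linked sections.

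What the defence does not remove is the conjunction. Even if *less* means *worse*, harm is still only half of the written criterion. The other safeguards bring events to notice; they do not say when the trial may be stopped.

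**Conclusion.** The concern holds in a limited form. As written, the plan's only study-level stopping criterion does not clearly authorise discontinuation on harm alone. Its direction is reversed for adverse outcomes and correct for outcomes where a low value is bad. It does not match the wording of the section it cites, and that section contains no criterion to take its place.

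The effect cannot be expressed as a probability or an error rate, since the plan gives no anticipated rates or thresholds. The conclusion on direction assumes a literal reading of *less*. The conclusion on the conjunction holds under the literal and the charitable reading alike. Neither conclusion implies that the committee would in practice fail to act. The point is that the written criterion should support such action without interpretation.

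**What to change.** Reconcile 7.2.1 with 5.4 in one paragraph that does two things:

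1. State the direction of concern for each monitored maternal and fetal outcome. For adverse outcomes this is higher than anticipated, as 5.4 already has it. For outcomes such as the 5-minute Apgar score it is lower.
2. Replace the joint condition, so that documented harm, or a concern for harm, is by itself a ground on which the DSMC or the investigators may consider discontinuing the trial.

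The sponsor and the DSMC should confirm the final wording, including what the anticipated level refers to for each outcome.

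The cost is one paragraph of protocol text, with matching DSMC wording and the IRB approval that 1.3 requires for any protocol change. Design, sample size and data collection are unaffected.

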7.2.2 Data Monitoring

The overall responsibility of data monitoring for the study is with the principal investigator. This includes ensuring that data are collected accurately, timely, and retained throughout the study on all participants. A member the Women and Newborn Research department will perform periodic reviews of the data to provide feedback to the investigator and research team. These reviews will be scheduled with the study team in advance.

Monitored Events

- Informed consent documents
- Inclusion/exclusion criteria
- Potential adverse events
- IRB reports and documentation
- Regulatory Documentation

Monitoring Intervals

• After the first five patients are enrolled, an initial review will be conducted to ensure that consent documents are appropriately reviewed and participants are appropriately enrolled.

Monitoring will occur at least quarterly of the events listed above under "Monitored Events."

Quality Assurance

Monitoring will occur at least quarterly to review data as described above. As often as possible the information listed above will be reviewed for all participants. If unable, a random selection of participants will be monitored.

To ensure appropriate consent, a Consent Documentation Form will be utilized for this study. This will document the informed consent process, review of required elements of consent, and allow for a double-check for staff to ensure that the proper document is used.

8 – STUDY TIMETABLE

